# LIST OF ABBREVIATIONS

ADT	Androgen depravation therapy
AE	Adverse Event
ALT	Alanine Aminotransferase
ALC	Absolute Lymphocyte Count
AST	Aspartate Aminotransferase
BUN	Blood Urea Nitrogen
BPI	Brief Pain Inventory
CBC	Complete Blood Count
CMP	Comprehensive Metabolic Panel
CR	Complete Response
СТ	Computed Tomography
CTCAE	Common Terminology Criteria for Adverse Events
DLT	Dose Limiting Toxicity
DSMB	Data and Safety Monitoring Board
ECOG	Eastern Cooperative Oncology Group
FACS	Florescence Activated Cell Sorting
H&P	History & Physical Exam
HRQOL	Health-related Quality of Life
HRPP	Human Research Protections Program
IHC	Immunohistochemistry
IV (or iv)	Intravenously
mRCC	Metastatic Renal Cell Cancer
MTD	Maximum Tolerated Dose
NCI	National Cancer Institute
ORR	Overall Response Rate
OS	Overall Survival
PBMCs	Peripheral Blood Mononuclear Cells
PD	Progressive Disease
PFS	Progression Free Survival
p.o.	peros/by mouth/orally
PR	Partial Response
PRN	"Pro re nata" or as needed
QL	Quality of Life
RR	Response Rate
RT	Room Temperature
SABR	Steriotactic Ablative Body Radiation
SAE	Serious Adverse Event
SBRT	Steriotactic Body Radiation Therapy
SD	Stable Disease

# Study Number - STU 012013-041

SPH	St. Paul Hospital
VAS	Visual Acuity Score
WBC	White Blood Cells

## STUDY SCHEMA

## STUDY SUMMARY

Title	A Phase II Trial of High Dose IL-2 and Stereotactic Ablative Body Radiation Therapy (SABR) for Patients with Metastatic Clear Cell Renal Cell Cancer (mRCC)		
Short Title	HD IL-2 and SABR for metastatic RCC		
Protocol Number	STU 012013-041		
Phase	Phase 2		
Methodology	Single Arm, open label.		
Study Duration	Six years (two years for enrollment and 4 years for follow-up).		
Study Center(s)	Single-center		
Objectives	To evaluate the improvement in response rate (RR) and complete response (CR) of mRCC after treatment with SABR and HD IL-2		
Number of Subjects	Average 33; maximum 38		
Diagnosis and Main Inclusion Criteria	Metastatic Clear Cell Renal Cell Carcinoma		
Study Product(s), Dose, Route, Regimen	HD IL-2 (brand name Proleukin), 600,000 U/kg q8h X 14 dose, IV infusion; SABR dose varying from 8Gy-20Gy in 1-3 fractions.		
Duration of administration	HD IL-2: 1 weeks/cycle; maximum of 2 cycles/course over three weeks; Maximum of three courses. SABR: 1-3 fractions over one week.		
Reference therapy	HD IL-2		

#### 1.0 BACKGROUND AND RATIONALE

#### 1.1 Disease Background

An estimated 64,770 cases of kidney cancer (RCC) will be diagnosed in the U.S. in 2012 with an estimated 13,570 deaths (SEER). There has been a steady 2-4% per year increase in the incidence of RCC since 1975 that is not explained by increased and improved imaging studies. Clear cell cancers are the most common variant of kidney cancers comprising up to 80% of RCC. The five-year survival rate for RCC patients is 70%, however, this is including the majority of patients with localized disease whose five-year survival is 91%. At the time of diagnosis approximately 30% of RCC patients have metastatic disease and another 30% of patients recur, whose five-year survival is less than 10%. Therefore, there remains a great need for improvement in the therapeutic management of metastatic clear cell RCC (mRCC).

RCC is a unique cancer that is well known for its immunogenicity. It is one of the first cancers in which immunostimulatory therapy, such as interferon and interleukin, has been shown to induce durable treatment response leading to FDA approval of HD IL-2 treatment for mRCC patients as early as 1992. Although HD IL-2 remains a first-line therapy for clear cell mRCC patients, only a small minority of patients exhibits complete response (CR). Strategies for enhancing the percentage of patients exhibiting a CR may prove to be the only hope in offering a definitive treatment for this patient population.

#### 1.2 Stereotactic Ablative Body Radiation (SABR)

Stereotactic ablative body radiation (SABR) is an emerging treatment paradigm defined in the American Society of Therapeutic Radiology and Oncology guidelines as a "treatment method to deliver a high dose of radiation to the target, utilizing either a single dose or a small number of fractions with a high degree of precision within the body" [1]. Potential indications for SABR include a broad spectrum of tumor types and locations. The safety and efficacy of SABR to multiple sites is excellent as documented in multiple studies [2-4].

Previous studies have demonstrated multiple immunogenic properties of radiation therapy (RT), especially when given at high doses such as with SABR [5, 6]. Since SABR is a highly focused therapy, it does not inherently immunocompromise the host. In addition, as opposed to conventional radiation fields, SABR is a highly focused therapy that spares the surrounding lymph nodes which are vital for an effective immune response. By not surgically removing the tumor, the body retains the antigen depot (dying tumor cells) within the host. Furthermore, since SABR causes local inflammation, dendritic cells (DCs) are attracted into the tumor. The antigen-presenting properties and the induction of immunogenic cell death by SABR are well documented [7]. SABR-induced tumor cell death is primarily via mitotic catastrophy or necrosis, both of which are known to be immunogenic cell deaths as opposed to apoptosis, which is immunologically tolarogenic [8]. In vivo studies have shown that radiation induces release of damage (or danger)-associated molecular patterns (DAMPs) such as HMGB1, HSP and calreticulin into the extracellular matrix and thereby promotes the recruitment and activation of antigen-presenting cells (APCs) such as DCs for antigen presentation [9-11]. Subsequently, the APCs migrate to the draining lymph nodes for the presentation of the antigens and efficiently present tumor antigens in the cell surface MHC molecules to T cells [12]. The T cells initiate an adaptive immune response resulting in antibody production and the expansion of cytotoxic T cells. These are delivered to both the primary and metastatic tumor sites. Increased trafficking of CD8+ T cells to both irradiated tumor and their draining lymph node has been demonstrated [12, 13]. Furthermore, RT causes a dose-dependent increase in MHC I tumor neo-antigen presentation by the tumor cells [14]. This, in conjunction with a demonstrated increase in FAS death receptors on the tumor cell surface in response to radiation, renders tumor cells particularly susceptible to CD8+ T cell-mediated cytotoxic attack [15, 16].

There is also evidence from both pre-clinical and clinical studies that RT, specifically at ablative doses typical of SABR, initiates and augments an immune response and can synergize

with immunotherapy [13, 17-20]. In the clinic, this effect of SABR has been documented by multiple case reports of the abscopal effect, where SABR to one site results in a systemic complete response of tumor regression at metastatic sites [21-23] including that in mRCC [24]. *In vivo* animal studies have demonstrated that this abscopal effect of RT is immune-mediated [25]. The abscopal effect of SABR was shown most recently by Postow et. al. in their NEJM report demonstrating that the abscopal effect was due to an increase in tumor-specific T-lymphocytes and a decrease in MDSC following the combination treatment of SABR and CTLA-4 immunotherapy in metastatic melanoma patient [23].

## 1.3 HD IL-2

IL-2 is a cytokine that is a potent growth factor for T cells. It exerts its activity by binding to the IL-2 receptor (IL-2R) present on the cell surface of T cells and leads to its autophosphorylation via JAK/STAT5-dependent pathways, eventually leading to activation and proliferation of the T cells [26]. Although the exact mechanism by which HD IL-2 results in the durable CR is not known, the discovery that recombinant IL-2 can have potent anti-tumor activity has been shown in murine models as early as 1980s [27]. The stimulatory effects of IL-2 have been demonstrated in multiple steps along the pathways required for a successful generation of adaptive and CTL-mediated anti-tumor response. For example, IL-2 is produced by the antigenpresenting cells (APCs) after they have phagocytosed dying tumor cells (or pathogens), presented their antigen in MHC class II and have bound to their corresponding T cell receptor (TCR) in the surface of CD4+ T cells [28]. In this setting, IL-2 is considered the third essential signal that is necessary for clonal expansion and effector function of T cells, the first being TCR recognition of antigen in MHC and the second being binding of costimulatory molecule CD 28 to B7 [26, 28]. Similarly, CD8+ CTL function is also critically dependent on IL-2 as shown by the experiments that their effector or cytotoxic function is limited in IL-2 or IL-2R-deficient mice [29-31]. IL-2 is postulated to increase trafficking of CTL to the extralymphatic sites of infection or tumor [26, 32]. IL-2 induces  $T_h1$  differentiation of CD4 T helper cells which leads to activation of macrophages. Th1 cells also activate antibody production by activating B cells. IL-2 is produced by Th1 cells in response to activation by DC that results in CD8 activation and proliferation [28]. A distinct mechanism of antitumor activity of IL-2 may be mediated by activation of natural killer (NK) cells [33].

While the exact mechanism of anti-tumor activity of HD IL-2 is unclear, seven phase II and multiple phase III trials have clinically proven the efficacy of IL-2 in inducing durable CR and PR in clear cell RCC patients. In contrast, molecularly targeted therapies fail to induce CR and do not cure patients. The reported RR for treatment with HD IL-2 (600,000-800,000 IU/kg q8h x 14 as tolerated) in multiple phase III trials ranges from 20% to 23.2% and the CR ranges from 7%-9% [34-36]. Among the patients who achieve CR, >80% remained disease free at last follow-up with a median survival over 10 years [34, 37, 38] suggesting a durable response or a cure of mRCC. Alternate schedules and decreased doses of IL-2 have been tried without any improvement in outcome [35, 36, 39]. Predictive immunologic markers would enormously aide clinicians in selecting patients who will respond to HD IL-2.

There is significant toxicity of HD IL-2 affecting multiple organ systems that requires ICU admission for the duration of administration. These side effects include hypotension, cardiac arrhythmias, metabolic acidosis, fever, nausea and vomiting, dyspnea, edema, oliguria and renal failure, neurotoxicity, and dermatologic complications including a mortality of up to 1. Alternate schedules and decreased doses of IL-2 have been tried without any improvement in outcome [35, 36, 39]. Predictive immunologic markers would enormously aide clinicians in selecting patients who will respond to HD IL-2 and spare the toxicity to those who will not.

#### 1.4 Rationale

The combination of HD IL-2 immunotherapy and SABR for the treatment of mRCC can be explained by both immunological and clinical rationales.

#### 1.4.1 Immunologic Rationale

There are multiple immunologic steps where SABR is expected to augment the immune response generated by IL-2 and vice versa. As discussed above, IL-2 stimulates T cell-mediated immune response in a non-specific manner. It is expected that SABR, inducing immunogenic tumor cell death, will be able to provide a specific direction to the immune response by initiating antigen presentation. Recruited and activated by the DAMPs and other changes brought on to the tumor micro-environment by radiation therapy, the APCs migrate to the lymph node for antigen presentation and T-cell activation. This is one of the first steps that will be augmented by the administration of IL-2 since the presence of IL-2 is critical for the successful activation of T cells by DCs [26, 28]. It is estimated that this step will take 2-3 days, which is why IL-2 treatment will be initiated within 2-3.5 days of SABR.

RT also increases TIL trafficking within irradiate tumors [12, 20]. IL-2 increases tumor vascularization, thereby decreasing hypoxia within tumors and making them more radiosensitive [40]. The radiosensitizing effect of IL-2 gene expression within tumors has also been objectively demonstrated *in vivo [41]*. The effect of increased vascularization by IL-2 also is expected to increase TIL and APC infiltration within all tumor sites. IL-2-mediated increase in CTL trafficking to the tumor sites, as described above, will work synergistically with this step in increasing TIL in both irradiated and non-irradiated sites of tumor.

The combination of RT and cytokine therapy with macrophage inflammatory protein-1 $\alpha$  has been shown to induce strong abscopal effect regardless of tumor type [42]. In fact, the combination of IL-2 and RT has also been explored in animal models and has shown improved local control of irradiated tumor and regression of non-irradiated tumors within the same mouse [43, 44].

NK cells are part of the immune system's innate defense against cancer and were first discovered because of their anti-tumor activity [45]. In fact, *ex vivo* expansion and re-infusion of autologous NK cells has shown to induce long-term remission in cancer patients [46]. Specific destruction of cancer stem cells has been demonstrated by NK cells [47]. Radiation therapy increases expression of retinoic acid early inducible-1 (RAE-1) in carcinoma cells, which binds to the NKG2D receptor present in NK cells and CTLs and leads to their activation [20, 48]. Interestingly, NK cells contain IL-2 receptors and are activated by IL-2 treatment [26], thereby suggesting another possible synergistic interaction of IL-2 and SABR in producing an anti-tumor effect mediated by NK cell activation.

Cytoreductive nephrectomy in mRCC has shown to occasionally induce regression of the metastatic foci [49]. It is hypothesized that this is secondary to an immune-mediated response. Two large randomized trials have demonstrated a survival benefit of nephrectomy followed by IFN- $\alpha$  in mRCC patients [50, 51]. In multiple settings, it has been demonstrated that a bulky tumor is able to produce immunosuppressants and induce proliferation of myloid-derived suppressor cells (MDSCs) leading to immune tolerance of the tumor [52, 53]. The cancer immunesurveillance hypothesis states that a tumor is only able to survive and grow large when it has successfully evaded the immune system [54]. Therefore, surgical excision, or in this case ablative radiation, of the bulky primary sites of disease can lead to decreased levels of MDSCs, immunostimulation and regression of metastatic foci.

#### 1.4.1 Clinical Rationale

As applied in concert with IL-2 in the present study, SABR is intended not only as a systemic cytoreductive agent but also an immunostimulant by antigen presentation. By aggressively cytoreducing the tumor burden prior to the outset of IL-2 treatment, in addition to maintaining the burden of death below the lethal threshold, the growth dynamics may be altered to render the remaining cells more susceptible to the immunotherapy, thereby converting more PR patients into CR. Therefore, the purpose of SABR would be three-fold: (1) It would irradiate sites of disease that are bulky and therefore resistant to immunotherapy and potentially serving as origins of further tumor spread and metastasis. (2) By decreasing the burden of disease below a threshold, SABR would reduce or eliminate immunosuppressive effects of tumor. (3) Simultaneously, SABR would act as an *in-situ* IL-2 STU012013-041, [name], Form A3, Mod\_49, 05-20-19

tumor vaccination by initiating antigen presentation and immunocyte infiltration, thereby acting synergistically with IL-2 in facilitating an effective immune response and eventually affecting PR, CR, disease progression and overall survival.

Metastatic RCC can be seen as composed of bulky sites of disease and innumerable micrometastatic disease sites that are below the resolution limit of radiographic imaging. Systemic therapies like cytokine therapy or newly emerging targeted therapies are often effective towards micrometastatic disease but less so to the bulky sites of metastasis which requires multimodality treatment. Therefore systemic therapies can result in response, but ultimately the tumors progress, resulting in declining quality of life and death from cancer. Historically, the use of local therapies such as surgical metastectomy or conventional radiation for a purpose other than palliation was ineffective since the tumor distribution was systemic. RCC is one of the few cancer sites where NCCN guidelines recommend cytoreductive nephrectomy and metastasectomy in selected stage IV patients, not only for palliative purposes but for potential survival benefit as well. Similarly, RCC is one of the few cancer sites that has demonstrated a survival benefit for metastasectomies. Multiple retrospective studies, and one recently published randomized trial, have demonstrated an overall survival benefit (five years at 32.5% versus 12.4%, p<0.001) of metastasectomy in RCC patients [55-57]. There is growing evidence that this new, potent, highly focused, and convenient form of radiation called SABR can dramatically debulk and even eradicate bulky tumor deposits as effectively as surgical metastasectomy while being non-invasive [2, 58-60].

Since SABR is shown to be immunostimulatory, and tumor debulking in mRCC has shown to impart survival benefit, the combination of SABR and immunotherapy is expected to be synergistic for mRCC. A combination treatment that offers eradication of the bulky progressive sites and simultaneously synergizes with the concurrent systemic treatment of immunotherapy to eliminate the micrometastatic disease is expected to improve outcome dramatically by increasing the PRs into CRs and non-responders into PRs.

Therefore, we propose a single-arm, open-label, phase II trial of HD IL-2 and SABR to multiple sites of bulky disease. The toxicities of HD IL-2 are significant and well known. Given the multiple studies demonstrating excellent safety profile of SABR, including our own departmental experience, there are limited concerns for additional toxicity when they are administered sequentially [2-4]. In fact, a phase I trial of HD IL-2 and SBRT in melanoma and RCC patients has proven the safety and feasibility of this regimen [61]. This small study showed a CT evidence of PR in 3 out of 5 (60%) and a PET CR in 1 out of 5 (20%) mRCC patients treated with HD IL-2 immediately after SBRT. Given the short duration of their median follow up (480 days) it remains to be seen how many mRCC patients remain disease free in the long run.

The primary endpoint of this study is to measure improvement in response rate (RR) and compare it to the historically reported data. As reported in three randomized trials, the RR for HD IL-2 in mRCC is 20%-23% (see below). A significant improvement on the historically reported RR would justify seeking a phase III trial to show the efficacy of this regimen in improving overall survival. The secondary objectives of this trial will measure progression-free survival (PFS), overall survival (OS), time to progression (TTP), duration of treatment response and tumor-specific immune response, each of which also has the potential to be used as justification for a phase III trial. In addition, the exploratory objectives will include correlation of the immune response to clinical outcome, exploration of immunologic biomarkers to predict response, improvement in health-related quality of life (HR-QoL) and cost effectiveness analysis. Given the high cost of HD IL-2, requiring multiple ICU admissions for patients, it will be worthwhile to explore the cost effectiveness of adding SABR in improving the outcome of HD IL-2 treatment alone and perhaps in decreasing the number of treatments required to achieve the same or improved RR, and then analyzing the improvement in HR-QoL, the quality-adjusted survival and cost effectiveness of this regimen.

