The SABR prescription dose will be delivered to the periphery of the planning target volume (PTV, see below for definitions). Investigators will have discretion in choosing from either of the biologically equivalent dose levels using one or three fractions, although a single fraction is preferred over three fraction treatments. Treating physician will have further discretion in selecting the number and location of sites to treat if >6 sites of disease are present. Maximum number of lesions treated is deemed as feasible per the treating radiation oncologist. Physician's will be **REQUIRED** to leave at least one site of disease for the purpose of measuring a radiographic response (see section 6.1) at a non-treated site, as this is part of the primary endpoint. If left untreated, this site can be treated once patient meets the definition of progressive disease (PD) (see section 6). To clarify the definition of "site", each site is an area or organ with active extracranial disease (</=3 in the liver = one site and </=3 in the lung= one site) identified by CT scan, or PET/CT, within 4 weeks prior to initiation of SBRT (up to 2 contiguous vertebral metastasis will be considered a single site of disease). For example: a patient with 4 right axillary lymph nodes, L1-L2 bone metastasis, 3 right lung lesions, 1 left lung lesion, 2 liver lesions, and T2-T3 bone metastasis would be defined as having 6 sites of disease. Preference should be given to the largest feasible disease site, symptomatic sites and sites where palliative and preventative (i.e. to prevent a pathologic fracture in weight bearing bone, impending cord compression, impending SVC compression etc.) indications are applicable. The gross target/tumor volume (GTV) should be at least 2cm^3 in size, corresponding to roughly a 1.5 cm diameter tumor. This is to ensure that adequate tumor volume and therefore adequate tumor cells (roughly 10^8 -10^9 cells/cm^3 [96]) are killed for antigen presentation. Treating physicians should choose their dose based on established planning guidelines at their center including their ability to respect normal tissue tolerance listed below. It is not required that all targets be treated with the same dose fractionation. A dose from the following table should be used:

	Total Cumulative Dose Encompassing 95% of Planning					
	Target Volume (Gy)					
Number of	Protocol Compliant Minor Deviation * MinorDeviation					
Fractions						

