## 6.0 Measurement of Effect

## 6.1 Antitumor Effect

For the primary endpoint, response and progression will be evaluated in this study using the new international criteria proposed by the Response Evaluation Criteria in Solid Tumors (RECIST) Committee [JNCI 92(3):205-216, 2000], which was also used by the two randomized trials of HD IL-2 being used as historic controls for this trial [35, 36]. The only change from RECIST v.1.1 being implemented in this study is a confirmation of new lesions or progressive disease (PD) by a second scan >6wks apart, based on the immune RECIST (irRC) criteria proposed by Wolchok. et. al that is appropriate for immune-related treatment response [91]. This is primarily because immune response often can take longer time as compared to chemotherapy before producing a radiographic response and during this time new lesions may arise which will eventually regress and if it were not for a second confirmation, these patients would be labeled to have failed therapy. In addition, the majority of mRCC responders to HD IL-2 usually produce a durable response (median response duration of 24 months), therefore, this change will not affect the outcome [35]. Additional criteria for bone lesions and clinical endpoints of pathologic fracture and cord compression are added to this study (see Section 6.1.4).

Changes in only the largest diameter (unidimensional measurement) of the tumor lesions are used in the RECIST v1.1 criteria outlined in http://www.recist.com/.

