#### 6.1.2 Disease Parameters

Measurable disease. Measurable lesions are defined as those that can be accurately measured in at least one dimension (longest diameter to be recorded) as  $\geq$ 10 mm with spiral (Helical) CT scan. All tumor measurements must be recorded in millimeters (or decimal fractions of centimeters).

Non-measurable disease. All other lesions (or sites of disease), including small lesions (longest diameter <20 mm with conventional techniques or <10 mm using spiral CT scan), are considered non-measurable disease. Bone lesions, leptomeningeal disease (patients excluded), ascites, pleural/pericardial effusions, lymphangitis cutis/pulmonis, inflammatory breast disease, abdominal masses (not followed by CT or MRI), and cystic lesions are all non-measurable.

Target lesions. All measurable lesions up to a maximum of 3 lesions per organ and 6 lesions in total, representative of all involved organs, should be identified as **target lesions** and recorded and measured at baseline. Target lesions should be selected on the basis of their size (lesions with the longest diameter) and their suitability for accurate repeated measurements (either by imaging techniques or clinically). A sum of the longest diameter (LD) for all target lesions will be calculated and reported as the baseline sum LD. The baseline sum LD will be used as reference by which to characterize the objective tumor response.

Note: Lesions receiving SABR will be called "treated lesion" which should not be confused with "target lesions" defined here for the for the purpose of radiographic measurement. Treated lesions and target lesions are mutually exclusive lesions. Therefore, treated lesions will not be used as target lesions for evaluating response. Since patients with ANY number of metastasis is eligible for this study, in the instance where patient has only one or few site of disease and all of them are treated, appearance of new lesions (either measurable or non-measureable) will constitute PD.

Non-target lesions. All other lesions (or sites of disease) including any measurable lesions over and above the 6 target lesions should be identified as **non-target lesions** and should also be recorded at baseline. Measurements of these lesions are not required, but the presence or absence of each should be noted throughout follow-up.

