#### 11.2 Sample Size and Accrual

The previous studies show that the maximum RR for mRCC patients treated with HD IL-2 is 23% [35]. We expect a >60% improvement in this rate leading to a 36.8% RR for mRCC patients when treated with SABR and IL2. The calculation of the sample size is based on the RR and Simon's optimal two-stage design will be used with  $(\alpha,\beta)=(0.20, 0.20)$  [120]. The RR of 23% is set as the lowest desirable rate and 36.8% is the rate we are targeting. We chose type I error of 0.20 and type II error of 0.20. That is, if the true response rate is less than 23%, the probability of wrongly accepting the treatment for further study is 20%, and if the true response rate exceeds 36.8%, the probability of wrongly rejecting it for further study is 20%. According to the optimal two-stage design, a maximum of 33 patients will be needed. In the first stage, 17 patients will be evaluated. If 3 or fewer responses are observed, then the trial will be terminated for futility. Otherwise an additional 16 patients (second stage) will enter the trial. Finally, if more than 9 responses are observed among 33 patients, then the regimen

(SABR+IL-2) may be considered as the experimental arm of a Phase III trial. The average sample size for this phase II trial is 26.2 patients, and the probability of early termination is 0.43 for a drug with response probability of 23%.

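### Response is counted only in unirradiated lesions but judged against an all-lesion 23% for HD IL-2, so the 20% type I error holds only if HD IL-2 alone gives 23% or less in those lesions

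*Combined protocol and SAP*

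**What the plan says.** **Which lesions are irradiated.** Section 4.1.1: "Preference should be given to the largest feasible disease site". Symptomatic sites and sites with a palliative or preventative indication share that preference. Irradiated tumours should be at least about 1.5 cm across, and at least one site must be left untreated so that response can be measured.

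**Which lesions are measured.** Section 6.1.2: "treated lesions will not be used as target lesions for evaluating response". Among the remaining lesions, targets are chosen by longest diameter, and a lesion of 10 mm on spiral CT is large enough.

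**How the criteria are described.** Section 6.1: "The only change from RECIST v.1.1 being implemented in this study is a confirmation of new lesions or progressive disease". The same paragraph says that the two randomized HD IL-2 trials serving as historical controls also used RECIST.

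**The benchmark.** Section 11.2: "The RR of 23% is set as the lowest desirable rate". It describes 23% as the maximum reported for HD IL-2. Section 1.3 gives a range of 20% to 23.2%.

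**The premise about bulk.** Section 1.4.1 (Clinical Rationale), on the first purpose of SABR: "It would irradiate sites of disease that are bulky and therefore resistant to immunotherapy".

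**The concern.** The trial has no control arm, so the 23% null carries the whole comparison. That figure describes response to HD IL-2 when lesions were not set aside by a SABR rule. In this trial the response sum is built from what SABR leaves, and where the preference for large sites is followed, those are the smaller lesions.

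If bulky lesions resist immunotherapy, as the rationale says, HD IL-2 alone could do better in the remaining lesions than in the full set, even if SABR did nothing outside its field. A go decision could then partly reflect which lesions were measured. The risk is that 10 responders in 33 are reported as an improvement over HD IL-2, and used to support a Phase III trial, when the comparison shows only response in unirradiated lesions.

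Sections 11.2 and 11.3 contain no null matched to the measured lesions and no sensitivity analysis. Section 6.1, by naming a single departure from RECIST and stressing that the historical trials used RECIST, invites the reader to treat the two rates as like for like.

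**Working it through.** **Inputs (Section 11.2).** Null 23%, target 36.8%, both error limits 0.20. Stage 1: 17 patients, stop at 3 or fewer responses. Stage 2: 16 more. Go if more than 9 of 33 respond.

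**Formula.** For a true response rate p in the measured lesions,

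P(go) = sum over x = 4 to 17 of P(X1 = x) × P(X2 ≥ 10 − x), with X1 ~ Bin(17, p) and X2 ~ Bin(16, p).

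**Step 1: reproduce the plan's figures.**
- Early termination at 23%: P(X1 ≤ 3) = 0.427 (stated 0.43).
- Expected sample size at 23%: 17 + (1 − 0.427) × 16 = 26.2 (stated 26.2).
- Type I error at 23%: 0.197 (limit 0.20).
- Power at 36.8%: 0.805 (target 0.80).

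The design is computed correctly for its inputs.

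**Step 2: keep the rule and vary the HD IL-2-alone rate in the measured lesions.** The documents do not give this rate. The values above 23.2% are assumptions chosen to show a range.

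| HD IL-2-alone rate in measured lesions | P(go) with no SABR effect outside its field |
|---|---|
| 20% (low end of cited range) | 9.9% |
| 23% (plan) | 19.7% |
| 23.2% (top of cited range) | 20.4% |
| 25% | 28.1% |
| 27% | 37.5% |
| 30% | 52.4% |

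P(go) passes 20% at a rate of about 23.1%, so a 23% starting rate leaves almost no margin. If the all-lesion rate is really 20%, the margin is about 23.1 − 20 = 3.1 percentage points.

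**Step 3: how many responders keep P(go) at or below 20% at each null.** Same first stage, n = 33:

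| Null | Responders needed | P(go) at that null | Power at 36.8% |
|---|---|---|---|
| 23% | 10 | 19.7% | 81% |
| 25% | 11 | 17.5% | 71% |
| 27% | 12 | 15.2% | 58% |
| 30% | 13 | 16.0% | 44% |

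Raising the go threshold would therefore cost considerable power at this sample size. That is a reason to qualify how a go is interpreted and leave the rule unchanged.

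**The case against.** Several points on the other side stand.

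- **The 20% is not an error.** Section 11.2 already ties it to a true rate below 23%, and at 23% it is right. A reader might infer that the stated error is simply too low. The documents do not support that, because they give no HD IL-2-alone rate for unirradiated lesions.
- **The premise is thin.** The rationale also says that systemic therapies are "often effective towards micrometastatic disease but less so to the bulky sites of metastasis", but the contrast there is with deposits too small to image. Those cannot be target lesions, so the sentence does not show that smaller measurable lesions respond better than larger ones. The statement that bulky sites are resistant remains, with no size threshold.
- **Part of the mechanism works at patient level.** Sections 1.4.1 (Immunologic Rationale and Clinical Rationale) also describe bulk as suppressing immunity generally. If SABR had no effect outside its field, that suppression could persist and hold back the remaining lesions too.
- **Large lesions are not always removed.** Size is one preference among several. Bone lesions are non-measurable under Section 6.1.2, so irradiating them takes nothing out of the sum of diameters.
- **There are offsets.** The null is near the top of the cited range. A patient with no measurable unirradiated lesion has no target-lesion route to partial response.
- **The historical trials are known here only at second hand.** Section 6.1 says that they used RECIST. It does not say how their target lesions were chosen or whether bulk had been removed beforehand.
- **The exclusion is disclosed and sensible.** It keeps local shrinkage from SABR from counting as systemic response.

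These points limit what can be said about size, and they make the direction a possibility and not a deduction. They do not make the benchmark match the measured lesions, and neither Section 11.2 nor 11.3 tells the reader that it may not.

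**Conclusion.** The concern holds in conditional form. The endpoint and its benchmark may rest on different sets of lesions, and the protocol's own statement about bulk gives a reason to think that HD IL-2 alone could exceed 23% in the lesions measured. The 20% error is valid only if that rate is 23% or less. Beyond that, the false-go probability of the unchanged rule is 28% at 25%, 38% at 27% and 52% at 30%. If the true rate is 20%, it is 10%.

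These probabilities are exact for each assumed rate. Which rate applies is unknown, so they are not an estimate of bias. A larger, specific inflation could be obtained by assuming a slope of response on lesion size, but the documents give no such slope and any figure would only return the assumption.

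The wording in Section 6.1 is inaccurate whatever the rate is. Barring irradiated lesions from the target set is a further departure that bears on comparability, and the same paragraph goes on to add bone and clinical criteria. Excluding irradiated lesions is not itself the fault. The fault is the unqualified use of 23%.

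**What to change.** 1. **Section 6.1.** Replace the claim of a single change. List the exclusion of irradiated lesions from the target set as a further departure from RECIST, and say that it affects comparability with the historical rate.
2. **Section 11.2.** State that the 20% error assumes HD IL-2 alone gives 23% or less in the lesions actually measured. Print the exact false-go rates of the unchanged rule (3/17, 9/33): 20% at 23%, 28% at 25%, 38% at 27% and 52% at 30%.
3. **Section 11.3.** Pre-specify that the observed response rate is read against nulls from 23% to 30%, for example using the table in step 3 of the working. A go that does not hold over that range is reported as response in unirradiated lesions, not as improvement over HD IL-2. Also describe the response rate by baseline size of the largest unirradiated target lesion, which Section 6.1.2 already requires to be measured.

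The cost is wording and one descriptive table, with no extra patients, no new scans and no change to the go rule. The downside is a less favourable stated false-go rate and a more limited claim from a marginal go.
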